## PROTOCOL SYNOPSIS

Title:	
CONTINUED ACCESS PROTOCOL  A Prospective, Multicenter, Single-Arm, Observational Study of the Safety and Clinical Performance of RES (Regenerative Epithelial Suspension) Prepared with the ReCell® Device Combined with Meshed Skin Graft in the Treatment of Acute Burn Injuries

Purpose:	
This Continued Access Protocol has been written to allow ongoing treatment of subjects at selected investigational sites while the marketing application for the ReCell® Autologous Cell Harvesting Device is under FDA review.
 
Data collected within this study will augment safety and effectiveness results from previous Investigational Device Exemption (IDE) studies using the ReCell® device, increasing the available clinical evidence for the application of RES (Regenerative Epithelial Suspension) prepared from the ReCell® device as an adjunct to meshed grafts in subjects with acute thermal burn injuries requiring skin grafting for closure.

Design:	
This is a prospective, multicenter, single-arm observational study. Patients 5 years or older with a total body surface area (TBSA) thermal burn injury between 5 and 50% (inclusive) who require autografting will be considered for participation in this study. The regenerative epithelial suspension (RES) prepared using the ReCell® device will be applied over skin grafts meshed more widely than conventional autografting. RES may also be applied to donor areas. Healing, scar outcomes, pain and treatment-related adverse events will be evaluated at follow-up visits. Data concerning the clinical performance and safety of the ReCell device will be collected.
 
Follow-up visits will be performed at 1, 2, 4, 8, 12, and 24 weeks post-treatment. Healing outcomes will be evaluated at all visits by direct visualization by the investigator. Scar outcomes will be evaluated at 12 and 24 weeks post-treatment using the Patient and Observer Scar Assessment Scale (POSAS) questionnaire. Treatment-related and serious adverse events will be captured throughout the study.
 
At all visits, the study treatment area and RES-treated donor area will be documented photographically.

Safety Outcomes:	
Safety will be assessed by evaluation of treatment-related and serious adverse events.

Clinical Performance Outcomes:	
Healing  Treatment and RES-treated donor area closure will be evaluated via direct visualization. Complete wound closure is defined as skin re-epithelialization without drainage, confirmed at two consecutive study visits at least 2 weeks apart by direct visualization by the investigator.

	
Scar Scar outcomes will be measured using the Patient and Observer Scar Assessment Scale (POSAS) questionnaire which includes a component for both investigator and patient scar assessment.
 
Treatment-area Pain Measured via a numeric scale (1-10) and then as a component of the POSAS beginning at Week 12.

Enrollment	Up to 60 patients may be enrolled at up to 15 investigational sites in the United States.
Statistical Consideration	
A sample size of 60 subjects will allow for continued access of the ReCell device during PMA preparation and FDA review. Additionally, a sample size of 60 subjects will allow for the detection of an adverse event with true probability of occurrence among RES-treated subjects of <math>\geq 5\%</math> with 95% probability, allowing for additional characterization of safety profile of the ReCell device.
 
Analyses of treatment area closure will be performed for the As Treated (AT) and Per Protocol (PP) populations. Data will be summarized using counts and percentages for healed/not healed, and an exact (Clopper-Pearson) two-sided 95% confidence interval for the true proportion will be presented.
 
The AT population includes all those enrolled into the study and treated with RES. The AT population will be the primary analysis population for the healing, POSAS and pain assessments.
 
The PP population includes all AT subjects who have no major protocol deviations. The PP population will serve as the secondary analysis population for the healing, POSAS and pain assessments.
 
For evaluation of healing, scars, and pain, it is anticipated that there will be minimal missing data. No imputation of missing data is planned.

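### The closure definition sets no condition on how closure was obtained, so an RES-treated area that is re-grafted, closed by Week 12 and closed again at the next visit counts as healed

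*Combined protocol and SAP*

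**What the plan says.** The Healing entry under Clinical Performance Outcomes in the Protocol Synopsis gives the rule: "Complete wound closure is defined as skin re-epithelialization without drainage, confirmed at two consecutive study visits at least 2 weeks apart". It covers two kinds of area: "Treatment and RES-treated donor area closure will be evaluated via direct visualization".

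The Design entry sets the timetable: "Follow-up visits will be performed at 1, 2, 4, 8, 12, and 24 weeks post-treatment". It adds: "Healing outcomes will be evaluated at all visits by direct visualization by the investigator".

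Under Statistical Consideration, the closure analysis is a single proportion: "Data will be summarized using counts and percentages for healed/not healed, and an exact (Clopper-Pearson) two-sided 95% confidence interval". No comparator, success threshold or analysis week is given for it. The primary population is As Treated (AT): "The AT population includes all those enrolled into the study and treated with RES". The secondary population is Per Protocol (PP): "The PP population includes all AT subjects who have no major protocol deviations". On missing data: "No imputation of missing data is planned".

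None of this text mentions graft loss, re-grafting or any other further closure procedure, or says how a subject who has one is classified.

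**The concern.** The definition looks only at the state of the skin on two visit dates. It does not ask whether the graft placed with RES closed the wound or a later operation did. If the area was grafted again, eventual closure says little about the study treatment, yet the subject enters the numerator on the same footing as one whose first graft took.

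The Purpose entry says that the data are to add to the effectiveness evidence for RES used with meshed grafts, and the Design entry says that the grafts are meshed more widely than usual. Whether that combination closes the wound without another graft is therefore a natural question for the closure proportion to answer. With a single arm, no control group is subject to the same classification, so nothing in the study would show how much of the proportion depends on second procedures.

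The same subjects also contribute POSAS scores at Weeks 12 and 24 and pain scores. After a re-graft these describe the second graft, but they would be summarised as results after RES.

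**Working it through.** **The plan's own figure.** The sample size rests on the chance of seeing at least one adverse event with a true rate of 5% among 60 subjects: 1 − 0.95^60 = 1 − 0.0461 = 0.954. The stated 95% is reproduced. It does not involve closure, so nothing below changes n = 60.

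**Step 1: which visit pairs can confirm closure.** The visits are from the Design entry and the 2-week minimum from the Healing entry.

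| Consecutive visits (weeks) | Gap (weeks) | Can confirm closure? |
|---|---|---|
| 1 and 2 | 1 | No |
| 2 and 4 | 2 | Yes |
| 4 and 8 | 4 | Yes |
| 8 and 12 | 4 | Yes |
| 12 and 24 | 12 | Yes |

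Week 12 is the last visit at which closure can first be seen and still be confirmed. An area still open at Week 12 and re-grafted afterwards has only Week 24 left and cannot meet the rule.

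**Step 2: apply the rule to a re-grafted subject.** Suppose that the graft is lost at Week 2, the area is re-grafted at Week 3, and it is dry and re-epithelialised at Weeks 8 and 12. The two visits are consecutive and 4 weeks apart, so every element of the definition is met. The subject received RES and so stays in AT. PP drops the subject only if the re-graft is called a major deviation, which the text does not say. The missing-data sentence has no bearing, because the healing data are observed. The subject is counted as healed.

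**Step 3: size.** Let n be the number of treated subjects, h the number with confirmed closure and no further procedure before it, and r the number who had such a procedure and then met the rule.

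- Proportion as written: (h + r)/n
- Proportion with those subjects as not healed: h/n
- Difference: r/n, which is never negative

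At n = 60 each such subject adds 1/60 = 1.7 points. The documents give neither a closure rate nor a re-graft rate, so the counts below are assumptions that show a range. The exact 95% limits are the 2.5% quantile of Beta(x, n − x + 1) and the 97.5% quantile of Beta(x + 1, n − x), where x is the number healed; the upper limit is 100% when x = n.

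| Healed as written (assumed) | r (assumed) | Healed after reclassification |
|---|---|---|
| 60/60 = 100% (94.0–100) | 3 | 57/60 = 95.0% (86.1–99.0) |
| 60/60 = 100% (94.0–100) | 6 | 54/60 = 90.0% (79.5–96.2) |
| 57/60 = 95.0% (86.1–99.0) | 1 | 56/60 = 93.3% (83.8–98.2) |
| 57/60 = 95.0% (86.1–99.0) | 3 | 54/60 = 90.0% (79.5–96.2) |
| 54/60 = 90.0% (79.5–96.2) | 3 | 51/60 = 85.0% (73.4–92.9) |
| 54/60 = 90.0% (79.5–96.2) | 6 | 48/60 = 80.0% (67.7–89.2) |
| 48/60 = 80.0% (67.7–89.2) | 6 | 42/60 = 70.0% (56.8–81.2) |

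The first two rows assume that every subject eventually closes. Subjects who are re-grafted and never reach confirmed closure are already not healed, so they do not enter r.

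**The case against.** The strongest reply is that the text is silent, and silence is not a decision. A reader might infer that the plan deliberately credits RES with closure by any route. It does not say so. Only synopsis text is available, and a fuller protocol or analysis plan may hold a rule that cannot be checked here. That stands as a limit on the finding. It does not remove it, because the rule as printed gives the result in Step 2.

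A second reply is that eventual closure, whatever further procedures were needed, is a legitimate quantity for an As Treated summary. That also stands. It is a reason to report both quantities and to say which one the healed/not healed figure is.

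A third is that failure would not be wholly hidden. Healing is assessed and photographed at every visit, and serious or treatment-related adverse events are collected throughout. Early non-closure would therefore be on record. But nothing says whether a re-graft is an adverse event, and nothing links adverse events to the healed count.

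Finally, the study is a descriptive continued-access study. No closure threshold or comparator exists, so no decision rule is distorted. That stands and limits the consequence to the estimate.

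**Conclusion.** The concern holds in a bounded form. As written, a subject whose treatment area is grafted or surgically closed again, is then closed by Week 12 and is closed at the next visit counts as healed in the As Treated analysis. Relative to treating that subject as not healed, the proportion can only rise, by about 1.7 points per subject if 60 are treated. The number of such subjects is unknown. The conclusion assumes that the definition is applied literally and that no rule on further procedures exists outside the synopsis.

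Stronger readings that the documents do not support:

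- **That any re-graft up to Week 24 can count as healed.** The visit schedule rules this out for an area still open at Week 12.
- **That the overstatement equals the re-graft rate.** It equals the proportion re-grafted and later confirmed closed. The two agree only if every re-grafted area goes on to confirmed closure.
- **That all outcomes are biased in favour of the device.** For POSAS and pain the direction is unknown, since scores from a twice-grafted area could be worse as well as better.
- **That re-grafting is the main way the treatment fails.** The documents say nothing about graft loss or its frequency, and the point does not depend on it.

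**What to change.** For the healed/not healed analysis, classify a treatment area as not healed if it has a further grafting or surgical closure procedure before confirmed closure. Apply the same rule to an RES-treated donor area, since the definition covers both.

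Record the date of each such procedure, and report the number and timing beside the closure proportion. Show closure regardless of further procedures as a sensitivity result, so that both quantities are visible. Present POSAS and pain with and without scores obtained after such a procedure.

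The cost is a clause in the definition, a dated yes/no field on the case report form, and a few extra summary lines. The sample size does not change. The downside is that the reported closure percentage may be slightly less favourable. The change governs how outcomes are classified and has no bearing on whether or when an area is re-grafted.

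### Does the two-visit closure rule leave the healed proportion undefined when a confirming visit is missed?

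*Combined protocol and SAP*

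**What the plan says.** All of the relevant text is in the Protocol Synopsis.

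- **Definition** (Clinical Performance Outcomes, Healing): closure must be "confirmed at two consecutive study visits at least 2 weeks apart by direct visualization by the investigator".
- **Schedule** (Design): "Follow-up visits will be performed at 1, 2, 4, 8, 12, and 24 weeks post-treatment". No later visit is listed. "Healing outcomes will be evaluated at all visits by direct visualization by the investigator".
- **Summary** (Statistical Consideration): "Data will be summarized using counts and percentages for healed/not healed". A two-sided 95% Clopper-Pearson interval goes with the proportion.
- **Population** (Statistical Consideration): "The AT population includes all those enrolled into the study and treated with RES". This population is the primary one for healing.
- **Missing data** (Statistical Consideration): little is expected, no rate is given, and "No imputation of missing data is planned".

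The synopsis does not say whether consecutive visits are scheduled or attended ones. It also does not say what happens to a subject whose confirming visit is missed.

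**The concern.** Two statements seem to pull apart. Suppose a subject is first seen closed at Week 12 and misses Week 24. Scoring that subject not healed keeps the full As Treated (AT) denominator but looks like setting a missing value to failure. Leaving the subject out avoids any imputation, but the denominator is then smaller than the AT population.

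A second case turns on one word. A subject closed at Week 8, absent at Week 12 and closed at Week 24 is confirmed if consecutive means attended visits, and unconfirmed if it means scheduled visits.

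If this were serious, two analysts could report different proportions from the same data, and the choice could be made after the results were seen. This is the only healing estimate for which the synopsis plans an interval, and the study is meant to add to the evidence from the earlier device studies.

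**Working it through.** **The plan's own figure.** The one figure that can be recomputed is the sample-size statement: the chance of seeing at least one adverse event of true rate 5% in 60 subjects. 1 − 0.95^60 = 0.954, which agrees with the stated 95%. It has no bearing on healing.

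**Which subjects are affected.** The visits at Weeks 1, 2, 4, 8, 12 and 24 are 1, 2, 4, 4 and 12 weeks apart. Take closure that is sustained once seen, and let one later visit be missed.

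| First seen closed | Confirmation lost, scheduled reading | Confirmation lost, attended reading |
|---|---|---|
| Week 1, 2 or 4 | never | never |
| Week 8 | if Week 12 is missed | never |
| Week 12 | if Week 24 is missed | if Week 24 is missed |
| Week 24 | always | always |

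The Week 24 row is not ambiguous. No visit has been missed, because none follows. The definition is not met, so the subject is not healed and nothing is imputed. That leaves the Week 8 and Week 12 rows.

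**How often.** The documents give no missed-visit rate. Assume each later visit is missed independently with probability m = 5%, 10% or 20%.

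- A Week 12 closure is lost with probability m on both readings: 5%, 10%, 20%.
- A Week 8 closure is lost with probability m on the scheduled reading, and m² on the attended reading: 0.25%, 1%, 4%.

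The expected number lost on the scheduled reading is m × N, where N is the number first closed at Week 8 or 12. An expected 3 needs N = 3/0.10 = 30 at 10% missed, or 3/0.20 = 15 at 20%. An expected 6 needs N = 60 at 10%, which is impossible if 6 of 60 never close, or N = 30 at 20%.

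**Effect on the estimate.** Assume 60 AT subjects, 6 never closed, and u seen closed but unconfirmed. Confirmed closures are 60 − 6 − u. Intervals are Clopper-Pearson 95%.

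| u | Scored not healed | Left out | Difference |
|---|---|---|---|
| 1 | 53/60 = 88.3% (77.4 to 95.2) | 53/59 = 89.8% (79.2 to 96.2) | 1.5 points |
| 3 | 51/60 = 85.0% (73.4 to 92.9) | 51/57 = 89.5% (78.5 to 96.0) | 4.5 points |
| 6 | 48/60 = 80.0% (67.7 to 89.2) | 48/54 = 88.9% (77.4 to 95.8) | 8.9 points |

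Counting these subjects as healed would give 54/60 = 90.0% (79.5 to 96.2), but that contradicts the two-visit definition and is not a fair reading. At u = 3 the 4.5-point difference compares with an interval 92.9 − 73.4 = 19.5 points wide.

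**Reading the sentences together.** The definition makes confirmation a condition of closure. The summary has two categories and no third for unconfirmed subjects. The primary population is everyone treated. A subject without a confirming visit has not met the definition and falls in the second category. That applies the definition; it does not fill in a value.

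**The case for a change.** The strongest case for a change is that the default is nowhere written down. An analyst could read the no-imputation sentence as making a missing confirmation a missing outcome, and drop the subject. An expectation of few missing data is not a rule for the subjects who do have them. Week 24 is the only visit that can confirm a Week 12 closure, and it follows the longest gap. Loss to follow-up after a single closed visit could also produce more cases than the single-missed-visit count suggests. A sentence of wording would cost no visits, data or patients.

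Part of this stands: the available-case reading is not excluded, and the meaning of consecutive is open. But a written rule would gain little.

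- Keeping every AT subject in the denominator and treating lack of confirmation as not confirmed only records what the text already points to.
- Choosing attended visits is a debatable trade-off. It rescues the Week 8 case by accepting 24 − 8 = 16 weeks with no assessment, during which a reopening could go unseen. The scheduled reading is at least as natural.
- Requiring closure to be first seen by Week 12 changes no count, since on this schedule every confirmed closure already meets it.
- Adding back subjects seen closed only at their last attended visit does not give an upper bound. It misses a subject closed at Weeks 1 and 2, only one week apart, who is then lost.

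**Conclusion.** No change to the plan is needed. This is a gap that analysts would fill sensibly, and the natural choice is the cautious one: unconfirmed subjects stay in the AT denominator as not healed, which can only lower the reported rate. Closure first seen at Week 24 is settled by the definition. What remains open is a missed confirming visit after a Week 12 closure and, on the scheduled reading only, a missed Week 12 visit after a Week 8 closure.

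The difference from leaving such subjects out is 1.5 points for one affected subject and 4.5 points for three, with largely overlapping intervals. Six would give 8.9 points, but that is hard to square with the plan's expectation of few missing data. These figures assume 60 treated subjects and 6 never closed; the documents give neither a closure rate nor a missed-visit rate.

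The study is single-arm and observational. The synopsis sets no healing hypothesis or threshold, and it bases the sample size on continued access and adverse-event detection. The conclusion rests on the Protocol Synopsis alone; fuller derivation rules elsewhere could only narrow the gap.

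### Does the 95% adverse-event detection figure overstate what a study of up to 60 subjects can deliver?

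*Combined protocol and SAP*

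**What the plan says.** All the relevant text is in the Protocol Synopsis.

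- **Enrollment:** "Up to 60 patients may be enrolled at up to 15 investigational sites in the United States". This is a maximum; no minimum is given.
- **Statistical Consideration, first reason for 60:** "A sample size of 60 subjects will allow for continued access of the ReCell device during PMA preparation and FDA review".
- **Statistical Consideration, second reason, introduced as an addition:** "a sample size of 60 subjects will allow for the detection of an adverse event with true probability of occurrence among RES-treated subjects of" 5% or more, with 95% probability. The stated aim is to characterise the device's safety profile further.
- **Statistical Consideration, populations:** "The AT population includes all those enrolled into the study and treated with RES". Its stated use is limited: "The AT population will be the primary analysis population for the healing, POSAS and pain assessments". Safety is not named there.
- **Purpose:** the protocol exists "to allow ongoing treatment of subjects at selected investigational sites while the marketing application for the ReCell® Autologous Cell Harvesting Device is under FDA review", and its data are to add to the results of earlier device studies.
- **Design:** treatment-related and serious adverse events are recorded over the whole study. RES goes over the meshed grafts in every case; use on donor areas is optional.

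**The concern.** Three features together make the 95% look fragile.

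1. The figure holds only with 59 or 60 treated subjects, the top two values the cap allows.
2. The cap counts patients enrolled, while the detection statement counts subjects treated with RES. Two enrolled but untreated subjects would put the study below 59, and the plan has no allowance for them.
3. Enrolment is linked to a regulatory period of unknown length, so it could close early.

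If far fewer than 59 were treated and a report still repeated the planning statement, a reader might take zero occurrences of some event as stronger evidence against a 5% incidence than the data give. Two further points seem to add weight. The two-sided exact 95% upper limit for 0 events in 60 is 5.96%, above 5%. And for donor-area events the denominator would be only those subjects whose donor areas received RES.

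**Working it through.** **Inputs.** From Statistical Consideration: n = 60, true event probability p = 0.05, stated detection probability 95%. The synopsis does not define detection; I take it as observing at least one case, which is an assumption. Treated numbers below 60 and any loss rate are also assumptions, because the documents give none.

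**Step 1: the plan's own figure.** P(at least one event) = 1 − (1 − p)^n = 1 − 0.95^60 = 0.9539. The plan says 95%, so it is reproduced.

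**Step 2: the minimum n.** ln(0.05)/ln(0.95) = 58.40, rounded up to 59. At 59 the probability is 95.15%; at 58 it is 94.90%. The threshold of 59 is right, but crossing it costs 0.25 percentage points.

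**Step 3: smaller treated numbers.** The third column is 1 − 0.05^(1/n).

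| Treated (n) | P(at least one event), p = 5% | Rate detected with 95% probability |
|---|---|---|
| 60 | 95.4% | 4.9% |
| 58 | 94.9% | 5.0% |
| 54 | 93.7% | 5.4% |
| 50 | 92.3% | 5.8% |
| 40 | 87.1% | 7.2% |
| 30 | 78.5% | 9.5% |

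The decline is gradual. Detection stays within two points of 95% down to 52 treated and first falls outside at 51 (92.7%).

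**Step 4: enrolled but not treated or observed.** Suppose each of 60 enrolled subjects is treated and observed with probability 0.95. The chance that at least 59 are is 0.95^60 + 60 × 0.05 × 0.95^59 = 19%. That sounds alarming only if 59 is treated as a cliff. The relevant quantity is overall detection. Each enrolled subject yields an observed event with probability 0.05 × 0.95 = 0.0475, so detection is 1 − (1 − 0.0475)^60 = 94.6%, or 0.4 points below the stated 95%. The assumption is also pessimistic, since it discards a subject lost late in follow-up whose earlier events would have been recorded.

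**Step 5: the 5.96% limit.** With 0 events in 60, the two-sided exact 95% upper limit is 1 − 0.025^(1/60) = 5.96%, which has 97.5% one-sided confidence. The counterpart of 95% detection is the one-sided 95% bound, 1 − 0.05^(1/60) = 4.87%, which is below 5%. The 5.96% therefore does not contradict the plan.

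**Step 6: what the wording commits to.** The detection sentence is conditional on 60 subjects, says whose event probability it means, and stands directly below the row that makes 60 a maximum. It states a property at full size. It does not say that 60 will be reached or that 95% applies to a smaller number.

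**The case for a change.** The strongest case for the concern is this. Detection is the only quantitative reason given for 60 and the only quantitative statement about safety in the supplied text. Exact intervals are specified for healing but not for adverse events, and no analysis population is named for safety. Keeping 59 treated with an assumed 5% untreated would need 63 enrolled (59/0.95 = 62.1, rounded up), above the cap. At 30 treated, the chance of missing a 5% event is 21% instead of 5%.

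Some of this stands. The minimum is 59, no enrolment floor is stated, and no figure is given for smaller numbers. Saying explicitly that 95% applies if 60 are treated would be a harmless clarification.

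The rest does not make a defect:

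- Early closure is inferred from the purpose statement. The supplied text has no rule ending enrolment at approval, and the access period covers preparation of the application as well as its review.
- A fall to 40 or 30 treated is hypothetical.
- The documents nowhere plan to read zero events as excluding a 5% incidence.
- The detection sentence is about RES-treated subjects overall and makes no donor-area claim.
- Intervals for adverse events and separate donor-area figures are reporting preferences. Only a synopsis is available, so it cannot be judged whether fuller text covers them.

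**Conclusion.** The concern does not hold. The plan's 95% is correct for the number it names (95.39% at 60), its denominator is stated, and the cap is visible beside it. Losing a few subjects changes the figure by a point or two at most (94.90% at 58, 93.7% at 54), and an assumed 5% loss from 60 enrolled leaves about 94.6%. A material drop needs about 40 treated or fewer (87.1%), which the documents give no reason to expect. Access is the first stated basis for 60; detection is a secondary, descriptive property in a single-arm study, and in the supplied text no hypothesis test, stopping rule or decision rests on it. Whatever number is treated can be reported, and the corresponding probability follows in one line.

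This conclusion assumes that detection means at least one observed event and that events occur independently with a common probability across subjects.
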